1.0 SYNOPSIS

TITLE	Phase II study of Nivolumab/Ipilimumab plus Cabozantinib in patients with unresectable advanced melanoma
SHORT TITLE	Nivolumab/Ipilimumab plus Cabozantinib in Advanced Melanoma
PHASE	II
OBJECTIVES	
Primary objective:
 
 1. To determine progression free survival (PFS) for nivolumab/ipilimumab plus cabozantinib in patients with unresectable advanced melanoma 
Secondary objectives:
 
 1. To determine the response rate of nivolumab/ipilimumab plus cabozantinib in patients with unresectable advanced melanoma 2. To determine the overall survival (OS) of patients with unresectable advanced melanoma treated with nivolumab/ipilimumab plus cabozantinib 3. To determine the safety profile of nivolumab/ipilimumab plus cabozantinib in patients with unresectable advanced melanoma 
Exploratory objectives:
 
 1. To determine associations between baseline tumor mutational burden (TMB), angiogenesis pathways, and immunophenotyping with clinical activity of nivolumab/ipilimumab plus cabozantinib in patients with unresectable advanced melanoma 2. To determine associations between baseline mutations in genes regulating anti-tumor immunity with tumor immunophenotype and clinical activity of nivolumab/ipilimumab plus cabozantinib in patients with unresectable advanced melanoma 3. To assess on treatment biopsy for evidence of increased immune infiltration, vascularization, and MHC expression to nivolumab/ipilimumab plus cabozantinib in patients with unresectable advanced melanoma
STUDY DESIGN	In this phase II advanced melanoma study, all patients will receive treatment with nivolumab/ipilimumab plus cabozantinib for a 12 week induction period followed by nivolumab plus cabozantinib maintenance to complete up to 2 years of therapy unless disease

	
progression, dose limiting toxicity, provider/patient decision or patient withdrawal of consent occurs. The primary endpoint is the one year PFS rate. Patients will have staging scans at baseline and every 12 weeks during the first 2 years on study. Safety evaluations including labs, EKG and history and physical will occur at each visit. Baseline tumor sample is required and on treatment biopsy will be optional of superficial tumor in the skin, subcutaneous tissue or lymph node that is palpable.


KEY ELIGIBILITY CRITERIA
	
Inclusion Criteria
 
 1. All patients must have unresectable stage IIIb-IIIId or IV melanoma by AJCC 8th edition. (Note: Patients with uveal melanoma are excluded from this study.) 2. Age \geq 18 and ECOG Performance Status of 0 or 1. 3. Measurable disease by RECIST 1.1 4. Baseline tumor specimen available. (Note: unless waiver is granted) 5. Recovery to baseline or \leq Grade 1 CTCAE v4 from toxicities related to any prior treatments, unless AE(s) are clinically nonsignificant and/or stable on supportive therapy. 6. Adequate organ and marrow function. 7. Capable of understanding and complying with the protocol requirements and must have signed the informed consent document. 8. Sexually active fertile subjects and their partners must agree to use medically accepted methods of contraception (eg, barrier methods, including male condom, female condom, or diaphragm with spermicidal gel) during the course of the study and for 4 months after the last dose of study treatment. 9. Female subjects of childbearing potential must not be pregnant at screening. 
Exclusion Criteria
 
 1. Prior treatment with anti-PD-1/PD-L1 therapy, anti-CTLA-4 therapy or cabozantinib. Prior adjuvant anti-PD-1 and/or anti-CTLA-4 therapy is allowed if relapse is greater than 6 months from last dose. 2. Receipt of any type of small molecule kinase inhibitor (including investigational kinase inhibitor) within 2 weeks before first dose of study treatment. 3. Receipt of any type of cytotoxic, biologic or other systemic anticancer therapy (including investigational) within 4 weeks before first dose of study treatment. 4. Radiation therapy for bone metastasis or brain metastasis within 2 weeks, any other radiation therapy within 4 weeks before first dose of study treatment. Systemic treatment with radionuclides within 6 weeks before the first dose of study treatment.

	
 5. Known brain metastases that are ≥ 10mm or cranial epidural disease unless adequately treated with radiosurgery and/or surgery (including radiosurgery). Eligible subjects must be neurologically asymptomatic and without corticosteroid requirement. Dexamethasone ≤ 2mg daily (or equivalent) will be allowed if discontinuation of corticosteroids is not feasible due to post-radiation effects and patient is asymptomatic. Patients with active, asymptomatic brain metastases that are < 10mm and no corticosteroid requirement will be allowed without radiosurgery or surgery. 6. History of active autoimmune disorder requiring immunosuppressive agents. Patients with autoimmune disorders considered low risk, such as vitiligo and thyroiditis, will be allowed. 7. Concomitant anticoagulation with coumarin agents (eg, warfarin), direct thrombin inhibitors (e.g., dabigatran), betrixaban, or platelet inhibitors (eg, clopidogrel). Allowed anticoagulants are the following: 
 a. Prophylactic use of Low-dose aspirin for cardio-protection (per local applicable guidelines) and low-dose low molecular weight heparins (LMWH) are permitted. b. Anticoagulation with therapeutic doses of LMWH or anticoagulation with direct factor Xa inhibitors rivaroxaban, edoxaban, or apixaban is allowed in subjects without known brain metastases who are on a stable dose of the anticoagulant for at least 1 week before first dose of study treatment, and who have had no clinically significant hemorrhagic complications from the anticoagulation regimen or the tumor. 8. The subject has prothrombin time (PT)/INR or partial thromboplastin time (PTT) test $\geq 1.3 \times$ the laboratory ULN within 7 days before the first dose of study treatment. 9. The subject has uncontrolled, significant intercurrent or recent illness. 10. Major surgery (eg, GI surgery, removal or biopsy of brain metastasis) within 8 weeks before first dose of study treatment. 11. Corrected QT interval calculated by the Fridericia formula (QTcF) > 500 ms per electrocardiogram (ECG) within 28 days before first dose of study treatment. 12. Pregnant or lactating females. 13. Inability to swallow tablets. 14. Previously identified allergy or hypersensitivity to components of the study treatment formulations. 15. Diagnosis of another malignancy within 2 years before first dose of study treatment, except for superficial skin cancers, or
--	---

	
localized, low grade tumors deemed cured and not treated with systemic therapy.
 
16. Subjects with a condition requiring systemic treatment with either corticosteroids (> 10 mg daily prednisone equivalents) or other immunosuppressive medications within 14 days of study drug administration. Inhaled or topical steroids, and adrenal replacement doses > 10 mg daily prednisone equivalents are permitted in the absence of active autoimmune disease.

STATISTICAL CONSIDERATIONS	
The primary endpoint for the study is 1 year landmark PFS rate. The historical control with nivo/ipi from the Checkmate 067 study is a 1 year PFS rate of ~50% [1]. The target for this study is 75% (improvement by 25%), which is deemed a clinically meaning improvement. This will require a sample size of 23 for a one sided alpha of 0.05 and the power of 0.80. A simon two stage approach will be utilized. The study will be stopped if there 7 or few subjects out of 14 subjects progression free at 1 year. If the study meets criteria for continuation to the second stage, an additional 9 subjects will be enrolled. In the final analysis, the null hypothesis will be rejected (i.e., accept the alternative hypothesis of improved efficacy with nivolumab/ipilimumab plus cabozantinib) if 16 subjects or more are progression free at 1 year of the 23 total subjects. Assuming a dropout rate of 15% during the time of study, up to 27 subjects will be enrolled.

TOTAL NUMBER OF SUBJECTS	27 enrolled subjects (23 subjects required for primary endpoint analysis)
ESTIMATED ENROLLMENT PERIOD	Estimated 18 months
ESTIMATED STUDY DURATION	Estimated 42 months (2 years beyond last patient enrolled)

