11 STATISTICAL CONSIDERATIONS

Simon's Two-Stage Design will be used in hypothesis testing for the primary endpoint of a 1 year PFS rate. Based on the Checkmate 067 data [1], a 1 year PFS rate in the historical control is assumed to be 50% (H0: PFS rate=50%). In this trial, a target 1 year PFS rate will be 75% (improvement by 25%, H1: PFS rate \geq 75%), which is deemed a clinically meaningful improvement. This will require a sample size of 23 for a one sided alpha of 0.05 and the power of 0.80. In the futility stage with the first 14 subjects, the study will be stopped if there are 7 or fewer subjects progression free at 1 year. In the final analysis, the null hypothesis will be rejected if 16 subjects or more are progression free at 1 year of the 23 total subjects. Assuming a dropout rate of 15% during the time of study, up to 27 subjects will be enrolled.

In the event of unplanned interim analyses are needed due to slow accrual or any other reasons, we will use the curtailing based SCPRT approach for statistical analysis [36].

The PFS rate in the final analysis will be calculated and a 2-sided Clopper–Pearson 95% confidence interval (CI) will be calculated. PFS and OS will be analyzed using Kaplan–Meier product-limit estimates. Median PFS and OS and the cumulative probability of PFS and OS will be presented with two-sided 95% CI if estimable.

Remaining analyses will be descriptive and exploratory in nature. TMB will be evaluated as a continuous variable and dichotomous breakdowns including previously reported high vs low status using a 21 nonsynonymous variants/MB cutoff [37]. PD-L1 status will use high/low cutoffs of 1% and 5% positive IHC rates [1]. Other variables will be analyzed based on published data or optimization of cutoffs. Statistical comparisons will be performed with SAS/R and looking to determine associations with biomarkers and clinical outcomes.

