13.2 The Georgetown-Lombardi Comprehensive Cancer Center Data Safety Monitoring Committee

The Georgetown-Lombardi Comprehensive Cancer Center DSMC will review:

- Adverse event summary report
- Audit results if applicable
- Data related to stopping/decision rules described in study design
- Study accrual patterns
- Protocol deviations

The Georgetown Lombardi Comprehensive Cancer Center (LCCC) will be responsible for the data and safety monitoring of this trial. As this study is an investigator initiated Phase II study using FDA approved agents it is considered a moderate risk study which requires real-time monitoring by the PI and study team and semi-annual reviews by the LCCC Data and Safety Monitoring Committee (DSMC). Documentation of DSMC reviews will be provided to principal investigator and sponsor. Issues of immediate concern by the DSMC will be brought to the attention of the sponsor-investigator and other regulatory bodies as appropriate. The sponsor and principal investigator will work to address the DSMC's concerns.

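### Waiting for all 14 one-year outcomes before stage 2 does not sit well with an estimated 18-month enrolment; planned curtailment of stage 1 would fix this without changing any decision

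*Combined protocol and SAP*

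**What the plan says.** The design is a Simon two-stage test of the 1-year PFS rate, 50% against 75%. For stage 1, with 14 subjects, Section 11 says that "the study will be stopped if there are 7 or fewer subjects progression free at 1 year". The Synopsis continues: "If the study meets criteria for continuation to the second stage, an additional 9 subjects will be enrolled". The null is rejected with 16 or more of 23 progression free, and after a 15% dropout allowance "up to 27 subjects will be enrolled".

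The Synopsis gives the enrolment period as "Estimated 18 months" and the study duration as "Estimated 42 months (2 years beyond last patient enrolled"). No monthly accrual rate is given. No section says whether accrual stops while stage 1 matures.

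Two provisions come close. Section 11 says that if "unplanned interim analyses are needed due to slow accrual or any other reasons, we will use the curtailing based SCPRT approach". Section 13.2 has the data and safety monitoring committee (DSMC) look at data bearing on the stopping rules, through "semi-annual reviews by the LCCC Data and Safety Monitoring Committee (DSMC"), and also asks the PI and study team to monitor in real time.

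On follow-up, treatment lasts up to 2 years (Section 7.2). Table 7-1, footnote 9, adds 2 years of follow-up after treatment stops. Section 7.3 follows PFS and survival to 5 years from the start of treatment.

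**The concern.** A futility look protects subjects only if it can be acted on before the remaining subjects are enrolled. Here the stage 1 outcome takes a year to observe, and the whole enrolment period is 18 months. If the decision waits for all 14 outcomes, either accrual is closed for most of the planned period or the look comes too late to limit enrolment. The plan does not choose, so sites could read it in opposite ways.

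At stake is enrolment of further subjects on a combination that may be no better than its historical control. Section 3.5 reports grade 3-4 events in 13 of 18 phase 1 subjects (72%). Those were genitourinary patients in a study that planned three dose levels, and Section 2.0 calls the safety profile acceptable, with 11% discontinuing for toxicity.

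A lesser matter is that the stated duration ends before the plan's own follow-up does.

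**Working it through.** **Plan's own figures.**
- Duration: 18 + 24 = 42 months, as stated.
- Design, by exact binomial sums (stop at 7 or fewer of 14, reject at 16 or more of 23): P(reject | 0.50) = 0.0462, P(reject | 0.75) = 0.8016, P(stop at stage 1 | 0.50) = 0.6047. The stated alpha and power are met.

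**Full hold, any accrual pattern.** The wait after the 14th entry is at least 12 months, so the open time is at most 18 - 12 = 6 months. The rate needed while open is 23/6 = 3.8 per month, or 27/6 = 4.5 per month.

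**No hold.** Assume even accrual of 27/18 = 1.5 per month. The 14th entry is at 14/1.5 = month 9.3 and its outcome at 9.3 + 12 = month 21.3, which is 3.3 months after enrolment closes. If 17 must be enrolled to give 14 evaluable (14/0.85 = 16.5), the outcome is at 17/1.5 + 12 = month 23.3. All 14 outcomes are in by month 18 only if the 14th subject enters by month 6, that is 14/6 = 2.3 per month early on.

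**When the count is already decided.** With 7 failures among 14, at most 14 - 7 = 7 can be progression free, so the stopping condition is certain. With 8 progression free at 1 year, it cannot be met. Exactly one of these two events must occur, so acting on whichever comes first gives the same decision as waiting.

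**Time of the 7th failure.** This was simulated under the null for trials that meet the futility rule, at 1.5 per month, with no hold and no dropout. Two PFS curves were used, both with 50% at 12 months:
- Exponential.
- Weibull with shape 0.25, the shape through the 49% at 1 year and 39% at 3 years that Section 3.3 gives for nivolumab/ipilimumab: ln[ln(1/0.39)/ln(1/0.49)]/ln 3 = 0.25. An exponential curve with 49% at 1 year would imply 0.49³ = 12% at 3 years.

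| Detection of progression | Exponential: call before month 18 | Exponential: mean spared of 27 | Weibull: call before month 18 | Weibull: mean spared of 27 |
|---|---|---|---|---|
| Exact event times | 89% | 6.1 | 97% | 11.6 |
| 12-weekly scans | 79% | 4.2 | about 95% | 8.8 |
| Scans plus 4-week confirmation | 70% | 3.4 | 92-93% | 7.8 |

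**Follow-up against 42 months, with 18-month accrual.** For the last subject, 2 years of treatment ends at 18 + 24 = month 42. Two further years off treatment ends at 42 + 24 = month 66. Five years from first dose is 18 + 60 = month 78.

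**The case against.** The strongest reply is that the rule is a count, and nothing in the plan forbids acting once the count is settled. This stands. A reader might infer that all 27 subjects must be enrolled before the rule can be applied. The documents do not support that: the 7th failure settles the matter before month 18 in most futile trials. But the plan does not make this the stage 1 procedure. Its only mention of curtailment concerns unplanned analyses.

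A reader might also infer that, with a hold, the calendar is too short by a fixed number of months. That does not follow. The 1.5 per month is 27/18, which presumes accrual open for all 18 months. If a hold was planned, 18 months implies 3.8 to 4.5 per month while open. The study is multicentre and states no rate, so this cannot be called infeasible.

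Nor do the documents show that the 3-year OS endpoint is compromised at month 42. No section sets a data cut there, Section 7.3 follows survival to 5 years, and Section 11 says that "the cumulative probability of PFS and OS will be presented with two-sided 95% CI if estimable". Finally, both periods are labelled estimates, and 42 months is defined as 2 years past the last entry, which matches maximum treatment.

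**Conclusion.** The point holds as a gap in how stage 1 is to be run, not as an error in the design or in the sum. A full hold leaves at most 6 of 18 enrolment months open, whatever the accrual pattern. Without a hold, a look that waits for all 14 outcomes comes at about month 21.3 and spares no enrolment, although the rule stops 60% of trials under the null. The month 21.3 figure rests on even accrual at 1.5 per month, which is an assumption.

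The benefit of curtailment also rests on that rate, on no dropout, and on the PFS curve and detection of progression, hence the wide ranges of 70-97% and 3-12 subjects. The steeper early fall suggested by Section 3.3 favours the upper part of each range. The duration gap (42 against 66 and 78 months) needs only the stated 18 months and is a matter of definition. The primary endpoint is covered: the last of 27 subjects reaches 1 year at month 18 + 12 = 30 without a hold.

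**What to change.** 1. Make deterministic curtailment the planned stage 1 rule. Declare futility once 7 of the 14 stage 1 subjects have died or progressed within 1 year, counting progression only when confirmed or unequivocal as in Section 7.5.7. Declare continuation once 8 are progression free at 1 year. Fix the 14 by order of entry among evaluable subjects, and keep SCPRT for unplanned looks. Sample size, boundaries, alpha, power and every stage 1 decision stay the same.

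   The cost is a running stage 1 event count that reaches the PI and the DSMC between semi-annual reviews. Section 13.2 already asks for real-time monitoring by the study team. Without that count much of the gain is lost: if it is seen only at months 6, 12 and 18 (assumed dates), the futility call is made by month 12 in 3-21% of futile trials under the exponential curve and 35-74% under the Weibull.

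2. As clarification, state whether accrual is held for the stage 1 decision, which is the sponsor's choice, and make the 18- and 42-month estimates match. A hold closes accrual for up to 12 months after the 14th entry; curtailment can shorten it.

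3. Say that the 42 months covers the last subject's maximum treatment period and not the follow-up in Table 7-1, footnote 9, and Section 7.3. Items 2 and 3 cost only wording.

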2.0 INTRODUCTION

Combination immune checkpoint blockade with nivolumab and ipilimumab demonstrated objective responses in 58% of patients with advanced unresectable melanoma in the Checkmate 067 study [1]. While responses and progression free survival (PFS) are superior with nivolumab/ipilimumab over monotherapy, not all patients have long-term benefit. Twenty four percent of patients had progressive disease as their best response and over 30% of patients progressed after initial disease control. At one year, the PFS rate was 49%. In addition, several patient subgroups had less clinical benefit as demonstrated by shorter progression free survival in patients with PD-L1 low tumors, high LDH levels, M1c disease, or greater than 3 disease sites. Other studies have also shown that patients with low interferon gamma gene expression scores or low baseline tumor immune infiltrate are less likely to have a response to standard anti-PD-1 based therapy [2]. Therefore, further immunotherapy strategies are needed.

Targeting vascular signaling in the tumor microenvironment, along with other oncogenic pathways, can enhance the anti-tumor activity of immune checkpoint therapies. A phase 1 study ipilimumab in combination with the anti-VEGF antibody bevacizumab in patients with advanced melanoma demonstrated an increased response rate and longer median overall survival compared to historical data [3]. On-treatment tumor biopsies revealed activated vessel endothelium with extensive CD8+ and macrophage cell infiltration. Similarly, clinical trials of combination therapy with the VEGFR inhibitor axitinib plus pembrolizumab and bevacizumab plus atezolizumab have demonstrated markedly increased anti-tumor activity in patients with advanced renal cell carcinoma [4, 5]. In addition to increased immune cell infiltration, targeting VEGF/R can enhance T-cell priming and dendritic cell maturation, as well as increased MHC class antigen presentation on tumor cells, which can lead to greater anti-tumor immune responses [6-8].

Cabozantinib, an inhibitor of c-MET, VEGFR2, and other receptor tyrosine kinases (RTKs) may be able to further augment immune responses in combination with nivolumab plus ipilimumab. In a phase II study of cabozantinib 55% of patients with advanced melanoma demonstrated tumor regression in the first 12 weeks [9]. Our team performed biomarker analyses on baseline tumor samples from this study [[name], unpublished data]. Patients with tumor regression and stable disease had greater tumor mutational burden (TMB) than those with disease progression. The high TMB status has been associated with greater neoantigen exposure and clinical activity with immunotherapies [2], suggesting cabozantinib also functions as an immune agent in addition to its direct anti-tumor and anti-angiogenic activities. Other studies with cabozantinib have also demonstrated immune modulatory effects by decreasing Treg populations in the tumor microenvironment and by increasing cytotoxic lymphocyte and decreasing immunosuppressive myeloid cell levels in the peripheral blood [10, 11]. A phase I study of nivolumab/ipilimumab plus cabozantinib in a range of genitourinary malignancies demonstrated clinical activity and an acceptable safety profile with only 11% of patients discontinuing therapy due to toxicity [12].

We propose a single arm phase II study of nivolumab/ipilimumab plus cabozantinib in patients with advanced melanoma, along with correlative studies to assess biologic/immune activity and predictive biomarkers.

Hypotheses:

- 1) Nivolumab/ipilimumab plus cabozantinib will demonstrate greater clinical activity compared to either nivolumab/ipilimumab or cabozantinib alone (historical data) in patients with unresectable advanced melanoma.
- 2) Nivolumab/ipilimumab plus cabozantinib will demonstrate clinical activity in patients with low tumor PD-L1 and interferon (IFN) gamma gene expression profile (GEP) scores, particularly those who have high TMB.

3.0 BACKGROUND INFORMATION

3.1 Anti-PD-1 monotherapy in advanced melanoma

Nivolumab (BMS-936558; anti-PD-1 monoclonal antibody) is a fully human monoclonal immunoglobulin (Ig) G4 antibody that binds to the PD-1 cell surface membrane receptor, a negative regulatory molecule expressed by activated T and B lymphocytes. Inhibition of the interaction between PD-1 and its ligands promote immune responses and antigen-specific T cell responses to both foreign and self antigens. PD-1 receptor blockade by nivolumab is an effective approach for immunotherapy of a variety of solid tumors. Results from a Phase 1/2 study (CA209-003) indicated that nivolumab was active in multiple tumor types including advanced melanoma, non-small cell lung carcinoma (NSCLC) and renal cell carcinoma (RCC) [13]. Clinical activity was noted across a range of doses (0.1 mg/kg, 0.3 mg/kg, 1 mg/kg, 3 mg/kg, 10 mg/kg). Among 106 subjects with advanced melanoma who received nivolumab and were evaluable for response, the preliminary objective response rates (ORR) were 6/17 (35%), 5/18 (28%), 11/34 (32%), 7/17 (41%), and 4/20 (20%) for melanoma subjects treated at 0.1, 0.3, 1, 3, and 10 mg/kg, respectively [14]. Duration of response range from 3.6 to 11.2, 1.8 to 9.2, 1.9 to 24.9, 9.2 to 22.4, and 17.0 to 25.7 months in the melanoma subjects treated at 0.1, 0.3, 1, 3, and 10 mg/kg, respectively. Stable disease \geq 24 weeks occurred in an additional 1/18 (6%), 4/34 (12%), 1/17(6%) melanoma subjects at 0.3, 1, and 3 mg/kg, respectively. Finally, the PFS-24 week was 41%, 33%, 48%, 55%, and 30% in melanoma subjects treated at 0.1, 0.3, 1, 3, and 10 mg/kg, respectively.

In a Phase 3 trial (CheckMate 066), nivolumab monotherapy demonstrated an improvement in overall survival (OS) versus dacarbazine in treatment-naïve patients with BRAF wild-type tumors [15]. Follow-up of patients in this study has shown 2-year OS rates of 58% with nivolumab and 27% with dacarbazine. Frontline nivolumab monotherapy has also been studied in the CheckMate 067, which included both BRAF wild-type and mutant melanoma [1]. The objective response rate was 44% with 3 year PFS and OS rates of 32% and 52% respectively.

Pembrolizumab (MK-3475) is a selective humanized monoclonal antibody (mAb) of the IgG4/kappa isotype designed to directly block the interaction between PD-1 and its ligands, PD-L1 and PD-L2. The variable region sequences of a mouse antihuman PD-1 antibody were attached into a human IgG immunoglobulin with a stabilizing S228P Fc alteration, where the IgG4 subtype does not engage Fc receptors or activate complement, therefore avoiding cytotoxic effects of the antibody when it binds to the T cells that are intended to activate. Results from a Phase 1 study (KEYNOTE 001) demonstrated that pembrolizumab is active in patients with advanced melanoma [16]. In the overall population, the objective response rate was 33%, with

74% of responses ongoing at the time of data cut. For treatment naïve patients, the objective response rate was 45% and 12 month PFS rate was 54%.

Similarly, the randomized KEYNOTE 006 study confirmed the efficacy of pembrolizumab in advanced melanoma patients, demonstrating superiority over ipilimumab [17]. In the treatment naïve population, the objective response rate was 47% by immune-related response criteria (irRC) and the 12-, 24-, and 36-month PFS rates were ~45%, 34%, and 31%, respectively.

Overall, anti-PD-1 monotherapy with pembrolizumab and nivolumab have been well tolerated. The most common adverse events include fatigue, pruritus, rash, diarrhea, nausea, and arthralgias [1, 16]. Most are low grade events that do not require treatment interruption or discontinuation. Severe treatment related adverse events have been reported in up to 21% of patients treated with anti-PD-1 monotherapy [1]. The more common severe adverse events occurring in 1-4% of patients include fatigue, rash, diarrhea/colitis, and elevated transaminase levels/hepatitis. Refer to Table 3-1. Adverse events with anti-PD-1 and anti-CTLA-4 therapies are usually immune mediated events and specific treatment algorithms for management have been published [18].

Table 3-1. Treatment related adverse events (occurring in more than 5% of patients) on CheckMate 067.

Event	Nivolumab plus Ipilimumab (N=313)		Nivolumab (N=313)		Ipilimumab (N=311)	
	Any Grade	Grade 3 or 4	Any Grade	Grade 3 or 4	Any Grade	Grade 3 or 4
number of patients with event (percent)						
Any treatment-related adverse event	300 (96)	184 (59)	270 (86)	67 (21)	268 (86)	86 (28)
Rash	93 (30)	10 (3)	72 (23)	1 (<1)	68 (22)	5 (2)
Pruritus	112 (35)	6 (2)	67 (21)	1 (<1)	113 (36)	1 (<1)
Vitiligo	28 (9)	0	29 (9)	1 (<1)	16 (5)	0
Maculopapular rash	38 (12)	6 (2)	15 (5)	2 (1)	38 (12)	1 (<1)
Fatigue	119 (38)	13 (4)	114 (36)	3 (1)	89 (29)	3 (1)
Asthenia	30 (10)	1 (<1)	25 (8)	1 (<1)	17 (5)	2 (1)
Pyrexia	60 (19)	2 (1)	21 (7)	0	21 (7)	1 (<1)
Diarrhea	142 (45)	29 (9)	67 (21)	9 (3)	105 (34)	18 (6)
Nausea	88 (28)	7 (2)	41 (13)	0	51 (16)	2 (1)
Vomiting	48 (15)	7 (2)	22 (7)	1 (<1)	24 (8)	1 (<1)
Abdominal pain	26 (8)	1 (<1)	18 (6)	0	28 (9)	2 (1)
Colitis	40 (13)	26 (8)	7 (2)	3 (1)	35 (11)	24 (8)
Headache	35 (11)	2 (1)	24 (8)	0	25 (8)	1 (<1)
Arthralgia	43 (14)	2 (1)	31 (10)	1 (<1)	22 (7)	0
Increased lipase level	44 (14)	34 (11)	27 (9)	14 (4)	18 (6)	12 (4)
Increased amylase level	26 (8)	9 (3)	20 (6)	6 (2)	15 (5)	4 (1)
Increased aspartate aminotransferase level	51 (16)	19 (6)	14 (4)	3 (1)	12 (4)	2 (1)
Increased alanine aminotransferase level	60 (19)	27 (9)	13 (4)	4 (1)	12 (4)	5 (2)
Decreased weight	19 (6)	0	10 (3)	0	4 (1)	1 (<1)
Hypothyroidism	53 (17)	1 (<1)	33 (11)	0	14 (5)	0
Hyperthyroidism	35 (11)	3 (1)	14 (4)	0	3 (1)	0
Hypophysitis	23 (7)	5 (2)	2 (1)	1 (<1)	12 (4)	5 (2)
Decreased appetite	60 (19)	4 (1)	36 (12)	0	41 (13)	1 (<1)
Cough	25 (8)	0	19 (6)	2 (1)	15 (5)	0
Dyspnea	36 (12)	3 (1)	19 (6)	1 (<1)	12 (4)	0
Pneumonitis	22 (7)	3 (1)	5 (2)	1 (<1)	5 (2)	1 (<1)
Treatment-related adverse event leading to discontinuation	123 (39)	95 (30)	37 (12)	24 (8)	49 (16)	43 (14)

